2.2.1 BIOSS® Registries

In the first-in-man trial 60 patients from three countries were enrolled (mean age 66.4 ± 11 years, 28.3% of female). There were 21.7% of patients with NSTE-ACS, 78.3% with hypertension, 38.3% with diabetes, 28.3% had previous MI, and 46.7% and 10% underwent prior revascularization, respectively, PCI and coronary artery bypass graft. At 12 months, the cumulative major adverse cardiovascular events rate was 11.7%. During follow-up (11 ± 1 months) there was 1 non-cardiac death (1.7%), 1 non-ST-elevated myocardial infarction (1.7%) due to restenosis and no case of stroke or in-stent thrombosis. Overall TLR was 8.3% (clinically driven TLR - 1.7%, angiographically driven - 6.6%). The side branch was treated with an additional classical DES implantation in 23.3% of cases²⁷.

In the second registry 74 cases with distal LM were analyzed. Seventy-three of 74 patients (aged 67 ± 9 years, 23% women, 20.3% NSTE-ACS, SYNTAX score 22.4 ± 4.4) were successfully treated with the BiOSS LIM® stent, with additional side branch classical DES

placement in 11 patients (14.9%). Periprocedural MI occurred in one (1.4%) patient. The 12-month MACE rate was 9.5% without cardiac death or definite stent thrombosis. TLR and MI rates were 6.8% (n=5) and 2.7% (n=2), respectively. This report showed that implantation of the dedicated bifurcation BiOSS LIM® stent in distal LM stenosis in patients with moderate SYNTAX score was safe and effective. Also, these results suggested that the sirolimus-eluting BiOSS LIM® stent have better results than the paclitaxel-eluting BiOSS Expert® stent. Moreover, this stent might offer an interesting option in coronary bifurcation treatment, especially when there is a large difference in the diameter between the main vessel and the main branch²⁶. The vast majority of implantations were possible using radial access (more than 90%) and 6F compatible equipment (including also LM cases). Rewiring of the SB after BiOSS® Expert stent implantation was relatively easy (lower device profile, and no guide wires criss-crossing or improper device orientation was observed. The device success rate was 100%.

2.2.2 Randomized clinical trials

The POLBOS I study was the first randomized clinical trial²⁵. The aim of POLBOS I trial was to compare bifurcation treatment with any classical DES to the dedicated bifurcation paclitaxel-eluting stent BiOSS Expert®. The second aim was to study the effect of final kissing balloon inflation (FKB) on clinical outcomes. Between October 2010 and January 2013, 243 patients with stable coronary artery disease or non-ST-elevation acute coronary syndrome were assigned 1:1 to one of two treatment strategies: BiOSS Expert® stent versus classical DES implantation. Coronary angiography was performed at 12 months. The primary end-point was composite of cardiac death, MI, and target lesion revascularization (TLR) at 12 months. BiOSS Expert® was implanted in 120 patients (49.4%) and DES in 123. The target vessel was LAD (52% vs 70%) followed by LM (22% vs 15%). In DES Group 38.2% were paclitaxel-eluting stents. There were 3 stent implantation failures (2 in DES and 1 in BiOSS group). Side-branch treatment with DES was required in 10% of cases in both groups. At 12 months, cumulative MACE incidence was similar in both groups: 13.3% vs 12.2% (P=0.7). TLR rate was significantly higher in BiOSS Group comparing to DES, 11.5% vs 7.3% (P=0.02). In further analysis, when comparing BiOSS Group to only PES subgroup from DES, the rate of TLR in both groups was comparable (11.5% vs 10.6%, NS). Moreover, when comparing LM bifurcation vs non-LM bifurcation lesions BiOSS Expert® was significantly superior to DES in treatment of distal LM stenosis (TLR: 7.4% vs 11.1%, P=0.04). The rates of clinically-driven TLR in our study were markedly lower in BiOSS as well as in DES Groups, 5.8% and 3.2% (NS), respectively. This is comparable to the best results of DES in coronary bifurcation treatment.

Subgroup analysis regarding FKB versus no FKB revealed that in both groups (BiOSS Group and DES Group) FKB was related with higher rate of SB stenting, longer time of

fluoroscopy and treated lesions were more frequently localized in LM. However, in FKB subgroups there was significantly lower rate of restenosis in BiOSS Group (8.1% vs 13.2%, P<0.05) as well as in DES Group (4.9% vs 9.5%, P<0.05). Interestingly, in DES Group the rate of restenosis in FKB+POT subgroup was even lower (1/42, 2.4%). It strongly suggests to optimize the process of the BiOSS® stent implantation despite its design.

The POLBOS I trial established an important benchmark for future studies with new generations of BiOSS® stents eluting -olimus drugs and utilizing newer stent materials. Therefore the POLBOS II was the continuation of the concept of POLBOS I, where BiOSS LIM® was compared with regular DES. Worth stressing is the fact that interim analysis of POLBOS II also suggests, similarly to POLBOS I study, that a more aggressive protocol (FKB and POT) during BiOSS® stent implantation yielded better angiographic and clinical outcomes.

2.2.3 Study Aims

This protocol will establish clinical outcomes of the BiOSS LIM C in a left-main bifurcation population and compared with a pre-specified performance goal.

3 OBJECTIVE

To establish the safety and efficacy of the BiOSS LIM C with respect to Patient oriented Composite Endpoint (PoCE) at 12 months in a “real world” left-main bifurcation population and compared with a pre-specified performance goal.

**Since the sample size and power calculation of the POLBOS LM study is based on the outcome of the EXCEL trial as an objective performance goal, the in- and exclusion criteria, general recommendations for practice, treatment and (endpoint) definitions are similar to the EXCEL protocol as published in NEJM and referred as such.³*

4 DESIGN OF THE TRIAL

A prospective, multicenter single arm study in patients with an indication for distal unprotected left main revascularization (either isolated distal left main disease or associated with disease in other coronary arteries). The treatment strategy consists of contemporary PCI of the left-main bifurcation following diagnostic angiography demonstrating significant distal left main disease and Medina classification (using dedicated bifurcation QCA software to confirm Medina classification) and local Heart Team discussion applying the anatomic SYNTAX Score.

The BiOSS LIM C (Balton, Warsaw, Poland) will be used for treatment of the Left-Main bifurcation, according it's instructions for use. The Alex-Plus cobalt-chromium sirolimus eluting stent (Balton, Warsaw, Poland) will be used for treatment of distal left-main side branches according it's instructions for use (i.e. proximal segments of the left anterior descending and left circumflex arteries as well as the ramus intermedius if the latter vessel is part of a trifurcation).

The presence of a significant lesion (%DS \geq 50) in any of the left main bifurcation segments (i.e., distal left main, ostial LAD or ostial LCX) must be confirmed by the academic team core lab (Rotterdam, NL) using dedicated bifurcation QCA.. Pre-procedure iFR is mandatory to explore the physiological importance of the left main bifurcation. IVUS may be performed up to discretion of the investigator.

IVUS assessment post-stent implantation for optimization of BiOSS LIM C deployment in the left-main bifurcation is highly recommended (according to ESC guidelines, class IIA)². OCT assessment may be performed up to discretion of the investigator.

All other lesions (other than left-main bifurcations) will be treated with XIENCE family everolimus-eluting coronary stent systems.

e.g. XIENCE V, XIENCE PRIME, XIENCE Xpedition, Xience PRO (PRO, PRO 48, PRO LL en PROx), Xience ALPINE, XIENCE Sierra or any next generation of the XIENCE family everolimus-eluting coronary stent system.

Clinical data will be adjudicated by an independent Clinical Event Committee.

The patients will be followed through 12 months to assess the clinical status and major clinical events (with a potential for possible follow-up for a total of 3 years).

5 ENDPOINTS

5.1 Primary Endpoint

The primary endpoint for this trial is defined as the patient-oriented composite endpoint (PoCE) at 12 months post-procedure. PoCE is a composite measure of

- All-cause mortality
- Stroke (modified Rankin Scale (mRS≥1)
- Any Myocardial Infarction* (includes nontarget vessel territory)
- Any unplanned revascularization for ischemia (includes all target and nontarget vessels)

5.2 Secondary Endpoints at all follow-up visits/contacts

1. Composite Endpoints

- Patient Oriented Composite Endpoint (PoCE) defined as the composite of all-cause death, stroke, any MI*, and any revascularization (for all follow-up contacts other than 12 months)
- Target Vessel Failure (TVF) defined as cardiac death, TV MI*, and clinically indicated target vessel revascularization
- TLF (DoCE) defined as cardiac death, TV MI* and clinically-indicated target lesion revascularization (DoCE will be reported both including the left-main target lesion only and all target lesions)

2. Mortality

- All death
- Cardiac death
- Non-cardiac death (vascular and non-cardiovascular)

3. Stroke

- All
- Ischemic
- Hemorrhagic

4. Myocardial Infarction*

- All MI (periprocedural, spontaneous, Q-wave and non Q-wave),
- Target Vessel/ Non-Target Vessel MI

5. Revascularization

- Any revascularization
- Target Lesion revascularization (TLR) (any, clinically-indicated TLR, non-clinically indicated TLR) TLR will be reported both including the left-main target lesion only and all target lesions)
- Target Vessel revascularization (TVR) (any, clinically-indicated TVR, non-clinically indicated TVR)
- Non-Target Vessel revascularization

6. Stent thrombosis according to ARC classification

* Definition EXCEL study (APPENDIX I: Definitions)

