	
coronary arteries).
 
The treatment strategy consists of contemporary PCI of the left-main bifurcation following diagnostic angiography demonstrating significant distal unprotected left main disease and local Heart Team discussion applying the anatomic SYNTAX Score.
 
The presence of a significant lesion (%DS\geq50) in any of the left main bifurcation segments (i.e., distal left main, ostial LAD or ostial LCX) must be confirmed by the academic team core lab (Rotterdam, NL) using dedicated bifurcation QCA. Pre-procedure iFR is mandatory to explore the physiological importance of the left main bifurcation. IVUS pre-procedure may be performed up to discretion of the investigator.
 
IVUS assessment post-stent implantation for optimization of BiOSS LIM C deployment is highly recommended according to ESC guidelines (Class IIa (Level of Evidence: B)^{1, 2}
 
The patients will be followed through 12 months to assess the clinical status and major clinical events with a potential for additional follow-up to 3 years.

Number of Patients	A total of 260 patients will be enrolled to receive treatment with the BiOSS LIM C study device.
Investigational Sites	Approximately 15 sites in Europe will participate.
Primary Endpoint	
Primary endpoint:
 
The primary endpoint for this trial is defined as the patient-oriented composite endpoint (PoCE) at 12 months post-procedure.
 
PoCE is a composite measure of:
 
 - All-cause mortality - Stroke (modified Rankin Scale (mRS\geq1)) - Any Myocardial Infarction (MI)* (includes nontarget vessel territory) - Any unplanned revascularization for ischemia (includes all target and nontarget vessels)

	
*Definition EXCEL study (APPENDIX I: Definitions)

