Secondary Endpoints	
Secondary Endpoints (evaluated at each follow-up visit/contact)
 
 1. Composite Endpoints 
 • Patient Oriented Composite Endpoint (PoCE) defined as the composite of all-cause death, stroke, any MI*, and any revascularization (for all follow-up contacts other than 12 months) • Target Vessel Failure (TVF) defined as cardiac death, TV MI*, and clinically indicated target vessel revascularization • Device Oriented Composite Endpoint (DoCE)/TLF defined as cardiac death, TV MI* and clinically-indicated target lesion revascularization (DoCE will be reported both including the left-main target lesion only and all target lesions) 2. Mortality 
 • All death • Cardiac death • Non-cardiac death (vascular and non-cardiovascular) 3. Stroke 
 • All • Ischemic • Hemorrhagic 4. Myocardial Infarction* 
 • All MI (periprocedural, spontaneous, Q-wave and non Q-wave), • Target Vessel/ Non-Target Vessel MI 5. Revascularization 
 • Any revascularization • Target Lesion revascularization (TLR) (any, clinically-indicated TLR, non-clinically indicated TLR). (TLR will be reported both including the left-main target lesion only and all target lesions) • Target Vessel revascularization (TVR) (any, clinically-indicated TVR, non-clinically indicated TVR) • Non-Target Vessel revascularization 6. Stent thrombosis according to ARC classification

	
*Definition EXCEL study (APPENDIX I: Definitions)

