7.6 Staged procedures

Procedural "staging" in PCI subjects is defined as a planned elective second PCI procedure at a separate setting to optimally complete the PCI. The criteria for staging are left to the operator's best judgment. Given the complexity of the ULMCA patients it is anticipated that a substantial number of patients may fall into the category of staged procedures.

In general, the decision to stage is based on the overall extent and complexity of coronary disease, the case complexity (intra-procedure difficulty encountered by the operator), the duration of the procedure, assessment of radiation exposure, the total volume of contrast utilized, the clinical stability of the subject, and other subject-related factors (diabetes, renal function, etc.).

If the patient requires a staged procedure, this should be documented at the time of the index procedure and the reason(s) for staging must be documented in the eCRF and source documents. Furthermore, the need for staging, and all specific lesions planned to be treated during the staged procedure should be declared beforehand in the eCRF at the time of initial baseline procedure. Stented segment(s) treated during the initial baseline procedure should not be treated again during the staged procedure.

The recommended timing of a planned staged procedure is optimally within 4 weeks, but it is strongly recommended that it is completed within 45 days. A staged procedure will not affect the original follow-up schedule.

The residual SYNTAX Score is an objective measure of the degree and complexity of residual stenosis after PCI. A correlation has been found between residual SYNTAX Score post PCI and mortality³⁶. In the POLBOS study it is recommended to attempt achieving a residual SYNTAX Score ≤ 8 post PCI.

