- *When biomarker levels are stable or falling*, there should be new CK-MB elevation by an absolute increment of $\geq 10 \times \text{ULN}$ (or $\geq 70 \times \text{ULN}$ for cTnI or T) from the previous nadir level
- *When biomarker levels have not been shown to be stable or falling*, there should be a further rise in CK-MB or troponin beyond the most recently measured value by an absolute increment of $\geq 10 \times \text{ULN}$ in CK-MB or $\geq 70 \times \text{ULN}$ in cTn plus new ST-segment elevation or depression plus signs consistent with a clinically relevant MI, such as new onset or worsening heart failure or sustained hypotension.

While not currently recommended as part of this definition, use of post-CABG ECGs, indices of hemodynamic instability, and imaging studies demonstrating new wall motion abnormalities are suggested to complement biomarker elevations post- CABG to improve specificity.

REVASCULARISATION

[Target Lesion]

A lesion revascularized in the index procedure (or staged procedure). The left-main target lesion extends from the distal left main stem to the end of the 5 mm proximal segments of the left anterior descending and left circumflex arteries as well as the ramus intermedius if the latter vessel has a vessel diameter of ≥ 2 mm.

[Target Vessel]

The target vessel is defined as the entire major coronary vessel proximal and distal to the target lesion including upstream and downstream branches and the target lesion itself. The left main

and any vessel originating from the left main coronary artery or its major branches is, by definition, considered a target vessel for the purposes of this trial (unless either the LAD or LCX are occluded at baseline and no attempt was made to revascularize these territories by PCI).

[Target Vessel-Non-Target Lesion]

The target vessel but non-target lesion consists of a lesion in the epicardial vessel/branch that contains the target lesion; however, this lesion is outside of the target lesion by at least 5 mm distal or proximal to the target lesion determined by coronary angiography.

[Non-Target Vessel]

For the purposes of this trial, the only possible non-target vessel would be the right coronary artery and its major branches that were not treated by PCI at the index procedure (unless either the LAD or LCX are occluded at baseline and no attempt was made to revascularize these territories by either PCI or CABG).

[Target Vessel Revascularization (TVR)]

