Target vessel revascularization is any repeat percutaneous intervention of the target vessel or bypass surgery of the target vessel.

[Target Lesion Revascularization (TLR)]

Target lesion revascularization is defined as any repeat percutaneous intervention of the target lesion or bypass surgery of the target vessel.

[Clinically-Indicated Revascularization (CI-TLR/TVR)]

Revascularization will be considered ischemia-driven if the target lesion diameter stenosis is $\geq 50\%$ by QCA and any of the following criteria for ischemia are met:

- Positive functional ischemia study including positive FFR/iFR corresponding to the area served by the target lesion; or
- Ischemic ECG changes at rest in a distribution consistent with the target vessel; or
- Typical ischemic symptoms referable to the target lesion; or
- IVUS of the target lesion with a minimal lumen area (MLA) of $\leq 4\text{mm}^2$ for non left main lesions or $\leq 6\text{mm}^2$ for left main lesions. If the lesions are de novo (i.e. not restenotic), the plaque burden must also be $\geq 60\%$; or
- FFR of the target lesion ≤ 0.80 or iFR of the target lesion ≤ 0.89 .

A target lesion revascularization for a diameter stenosis less than 50% might also be considered ischemia-driven by the Clinical Events Committee if there was a markedly positive functional study or ECG changes corresponding to the area served by the target lesion.

STENT THROMBOSIS

(ARC)⁴²

Stent thrombosis should be reported as a cumulative value at the different time points and with the different separate time points. Time 0 is defined as the time point after the guiding catheter has been removed and the patient left the catheterization lab.

Timing:

- Acute stent thrombosis*: 0 - 24 hours post stent implantation
- Subacute stent thrombosis*: >24 hours - 30 days post stent implantation
- Late stent thrombosis†: 30 days - 1 year post stent implantation
- Very late stent/ thrombosis†: >1 year post stent implantation

* Acute/subacute can also be replaced by early stent thrombosis. Early stent thrombosis (0 - 30 days) - this definition is currently used in the community.

† Including “primary” as well as “secondary” late stent thrombosis; “secondary” late stent thrombosis is a stent thrombosis after a target segment revascularization.

Categories:

- Definite
- Probable
- Possible

Definitions of each category are as follows.

- **Definite stent thrombosis**

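### PoCE counts only unplanned, ischemia-prompted revascularization at 12 months but every revascularization at other contacts, and no endpoint rule says how planned staged PCI is treated

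*Combined protocol and SAP*

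**What the plan says.** The synopsis and section 5.1 build the 12-month PoCE from death, stroke, MI and, as its last component, "Any unplanned revascularization for ischemia (includes all target and nontarget vessels". Section 9.4 repeats that component when it lists the primary endpoint events.

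Section 5.2 lists a secondary endpoint, also called PoCE, as the "composite of all-cause death, stroke, any MI*, and any revascularization (for all follow-up contacts other than 12 months". The synopsis has the same split: "any revascularization (for all follow-up contacts other than 12 months". Both limits on the component, that it be unplanned and that it be for ischemia, are absent. The contacts concerned are 30 days, 6 months and any optional follow-up to 3 years.

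Section 7.6 defines staging as a planned, elective second PCI that completes the treatment. Of its frequency it says that "it is anticipated that a substantial number of patients may fall into the category of staged procedures". The optimal interval is 4 weeks, and "it is strongly recommended that it is completed within 45 days". Staging and the lesions involved must be declared in the eCRF at the time of the index procedure.

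Appendix I defines target lesion, target vessel, TLR, TVR and clinically indicated revascularization. It does not define revascularization of any kind as an endpoint, and no section says whether a planned stage is an event.

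**The concern.** The bracket in 5.2 reads as if one endpoint were being reported at the remaining time points, but the component has changed. The change matters in this trial because planned second procedures are expected, and early. Under the literal text a patient with an uneventful stage on day 35 has a PoCE event at 6 months and none at 12 months. A cumulative rate for a single endpoint cannot fall; this series could.

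What is at stake is how the secondary PoCE values are read. A 6-month figure that includes planned completion of treatment would look like early failure, and an optional 3-year figure would mix the two. Section 8.3 also evaluates the secondary endpoints by one-stent versus two-stent approach, and 7.6 links staging to case complexity. If staging differs by technique (an inference; no rates are given), that exploratory comparison would be distorted. Whether stages count would be settled by the event committee or the analyst, not by the protocol.

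**Working it through.** **1. The plan's own figure, to see whether it is touched.** Section 8.2 gives a reference rate of 16.7%, margin 6.3%, one-sided alpha 5%, power 80% and 256 analyzable patients. The target is p0 = 0.167 + 0.063 = 0.230, with p1 = 0.167.

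n = [(1.645·√(0.230·0.770) + 0.842·√(0.167·0.833)) / 0.063]² = 255.04, so 256.

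The exact binomial test first reaches 80% power at n = 254 (0.805) and has power 0.789 at 256. The stated number reproduces closely. It rests on the 12-month definition, which already excludes planned procedures, so it does not depend on this point.

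**2. Does any text take staged PCI out of the 5.2 composite?**

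- Appendix I, target lesion: "A lesion revascularized in the index procedure (or staged procedure". This treats a stage as part of treatment, but it defines a lesion, not an event.
- Appendix I, TVR: "Target vessel revascularization is any repeat percutaneous intervention of the target vessel or bypass surgery of the target vessel". The word repeat, also used for TLR, largely protects those two endpoints. The 5.2 composite has no such word.
- Section 7.10 places adjudication of the type of revascularization under unscheduled procedures. It gives no rule for scheduled ones.
- Section 9.1 keeps planned hospitalization out of adverse events. That is a safety-reporting rule.
- Section 14.5 lists films of the index PCI and staged procedures apart from films of revascularizations. That is a data-flow rule.
- Section 8.5 mentions staging only to fix day 0.

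All of these except 8.5, which is neutral, point the same way. None is an endpoint rule.

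**3. Size under the literal reading (illustration).** Let s be the share of patients staged by 6 months and p the 6-month rate on the 5.1 definition. The documents give neither. I assume s of 5% to 20%, p of 8% to 12%, independence of the two, and N = 260.

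Excess = [1 − (1−s)(1−p)] − p = s(1−p)

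| s | p = 8% | p = 10% | p = 12% |
|---|---|---|---|
| 5% | 4.6 points (12.0 patients) | 4.5 (11.7) | 4.4 (11.4) |
| 10% | 9.2 (23.9) | 9.0 (23.4) | 8.8 (22.9) |
| 20% | 18.4 (47.8) | 18.0 (46.8) | 17.6 (45.8) |

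At 30 days, let f be the share of stages done by then and p30 the 5.1-definition rate. The excess is s·f·(1−p30). With f assumed 25% to 75% and p30 assumed 4% to 8%, s = 5% gives 0.05·0.25·0.92 = 1.2 points to 0.05·0.75·0.96 = 3.6 points.

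**4. When would the series fall?** The 6-month value exceeds the planned 16.7% at 12 months when s > 1 − 0.833/(1−p). That is 9.5%, 7.4% and 5.3% for p = 8%, 10% and 12%, or 25, 20 and 14 of 260 patients.

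**5. The opposite extreme.** If staged patients and event patients overlap fully, the excess is max(s, p) − p, which is zero while s ≤ p.

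**The case against.** The strongest reply is that 5.2 is shorthand. The same line also omits the modified Rankin threshold for stroke, which Appendix I supplies for stroke in general. The bracket may only avoid listing the primary endpoint twice. Staging is defined as completing the PCI, and 14.5 does not use the word revascularizations for the index PCI or for stages. A sensible event committee would probably not count a declared stage. Its charter, announced in 11.3, is not among the documents and may say so. Components are also reported separately, so inflation would be visible, and these endpoints carry no hypothesis test.

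Most of this stands. It makes the literal reading unlikely to be intended, and it confines the matter to clarity. It does not remove the conflict: the wider wording appears in both the synopsis and the body, and the committee is to classify events by the protocol's definitions, which contain no rule on stages.

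Two stronger readings are tempting and not supported.

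- A reader might infer that a stage in the right coronary artery must count as non-target vessel revascularization, since Appendix I limits the non-target vessel to the "right coronary artery and its major branches that were not treated by PCI at the index procedure". But a lesion treated at a stage is a target lesion there, and the vessel holding a target lesion is a target vessel. The appendix is ambiguous on this, not decisive.
- A reader might infer that the index PCI itself counts, because 8.5 starts the clock at consent. That would give every treated patient an event. Section 5.1 counts post-procedure, and 14.5 keeps the index PCI apart.

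**Conclusion.** The inconsistency is real: one name, two revascularization components, and no endpoint rule for planned stages. It should be corrected, but it reaches only descriptive secondary endpoints: PoCE away from 12 months and, through the Appendix I ambiguity, possibly non-target vessel revascularization.

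A reader might infer that the primary result is at risk. It is not. The primary endpoint, the 23.0% target, alpha, power, sample size, TVF and DoCE are all unaffected.

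The size cannot be derived from the documents. The figures in the working rest on assumed staging shares, event rates and timing, on independence, and on the literal reading that context disfavors. With full overlap the excess is zero while s ≤ p. If stages are left out, what remains is unplanned revascularization not done for ischemia, which should be small because 7.10 permits repeat procedures only with evidence of ischemia.

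**What to change.** 1. In 5.2 and in the synopsis, define PoCE at every contact as in 5.1. The Kaplan-Meier curve used for the primary analysis (8.1) then supplies the 30-day and 6-month values.
2. If a composite with revascularization of any kind is still wanted, keep it under a different name.
3. In Appendix I, state that staged procedures declared in the eCRF at the index procedure are not revascularization events, and say whether a right coronary artery treated only at a stage is a target or a non-target vessel. Other later procedures go to the event committee as now planned.

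The cost is wording in three places. No new data are needed, because 7.6 already requires the declaration, and no treatment or staging practice changes. The downside is that the wider composite is no longer reported as PoCE; it can be produced from the same data under its own name. The text should be settled before adjudication starts, so that the choice is not made with events in view.
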